### **Sampling method and subject recruitment**

Patient scheduled for elective OGDS in HUSM from April 2019 to December 2019 with the complaint of one or more of the following symptoms: Botherome postprandial fullness, early satiation, Epigastric pain or Epigastric burning are eligible to participate in the study. Patients who fulfilled exclusion criteria (History of upper gastrointestinal surgery, intestinal obstruction, patient with vomiting or mentally disable or who cannot give an informed consent) are ineligible.

If a patient fulfils the inclusion criteria, a suitable medical officer will discuss the trial with patient while reviewing patient in surgical outpatient clinic prior to OGDS. Patient will be approached again on the day of OGDS, if patient agree to participate in study, a written consent will be obtained. If patient refuse to participate in study, appropriate treatment and care still will be provided to patient. The consent form will provide information about the purpose of the study, the procedures to be followed,

risks and benefits of participation. If patient agree to participate in the trial, subject will be enrolled in the study. Method of recruitment in this study is direct recruitment of potential study participants.

Stratified permuted block randomization was used. Randomization sequence was created using <https://www.sealedenvelope.com/simple-randomiser/v1/lists> and is stratified by gender (female and male) with 1:1 allocation. Random block sizes of 6 is used. Subjects are randomized into either preprocedure plain water (group A) or preprocedure carbohydrate loading group (group B). Patients randomized into group A consume 250ml plain water and patients in group B consume 1 packet of resource (237ml, 53.6g carbohydrate and 9g whey protein). Both groups of patients consume the drink over 10 minutes. 2 hours after that, OGDS will be carried out.

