## **Methodology**

### **Research design**

This is a stratified (female, male) with balanced randomisation (1:1), single-blind (blind endoscopist, researcher enrolling and assessing participants), placebo-controlled, parallel-group study

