### **Data collection method**

All subjected planned for OGDS with the complain of one or more of the following symptoms: Bothersome postprandial fullness, early satiation, Epigastric pain or Epigastric burning and fullfill inclusion criteria are selected. Patients will be approached and be explained regarding the study in

surgical outpatient clinic prior to OGDS. Patient will be approached again on the day of OGDS, if agree to participate, an informed consent will be obtained. Informed consent will be obtained after explanation regarding the study and procedure again by researcher nurse

Allocation sequence is according computer generated random number list, it was prepared by an investigator with no clinical involvement in the trial. Allocation sequence was concealed from researcher enrolling and assessing participants. Allocation sequence will be sealed in sequentially numbered and opaque envelopes. A manila card will be placed inside envelop to render it impermeable to intense light. To prevent subversion of the allocation sequence, the name and I/C of the participant will be written on a book together with the series number on envelopes. The details in the book will be kept confidentially. After enrolled subject complete all baseline assessment, corresponding envelope will be enclosed by staff (who not involve in study) who prepare the drink. The staff need to ensure that the envelop still sealed when receive it. The staff will prepare the drink into identical container according to the assignment.

Subjects are randomised into 2 group: 1 group with 250cc plain water and another group give 1 packet resource(237ml). Subjects need to finish the drink over 10minutes. After that, subjects are not allow to leave endoscope room before OGDS done to prevent consumption of other drink or food.

2 hours after that, subject undergo OGDS. OGDS is done follow standard protocol.

1. Patient lies in left lateral position
2. Medication to numb the back of throats (spray) will be given to prevent gagging during the passage of the instrument
3. A plastic mouth guard is placed between the teeth to prevent damage to the teeth and endoscope.
4. The endoscope (also called a gastroscope) will be inserted through the mouthpiece

[figure not shown]
5. A small container or yankauer suction is placed close to the mouth of a patient to collect saliva during and after the esophagogastroduodenoscopy
6. Endoscope will be inserted along the middle line of the soft palate.

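### The randomisation is described as using random block sizes, but it has one fixed, disclosed size of 6, so 23–25% of allocations are certain to anyone who knows the earlier ones in a stratum

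*Protocol*

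**What the plan says.** Under Sampling method and subject recruitment, the Protocol states "Stratified permuted block randomization was used" and that the sequence "is stratified by gender (female and male) with 1:1 allocation". On block length it says only "Random block sizes of 6 is used". No second size appears anywhere in the document.

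The safeguards are under Data collection method. An investigator without clinical involvement prepares the list. "Allocation sequence was concealed from researcher enrolling and assessing participants", and "Allocation sequence will be sealed in sequentially numbered and opaque envelopes". The envelope is handled after baseline assessment by staff outside the study, and "The staff will prepare the drink into identical container according to the assignment". Research design calls the trial "single-blind (blind endoscopist, researcher enrolling and assessing participants"; participants are not listed among those blinded.

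The two drinks are plain water and a beverage that Product detail describes as fruit flavoured. After drinking, "subjects are not allow to leave endoscope room before OGDS done", which means a wait of 2 hours. Consent is taken on the day of the procedure.

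**The concern.** Random block sizes are used so that nobody can tell where a block ends. The Protocol claims that property, but with a single size it is absent. If the author meant randomly permuted blocks of 6, the size is still fixed. Block length, strata and ratio are all printed, so the only thing an observer lacks is the record of past assignments.

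Opaque envelopes stop anyone reading the next card. They do not stop deduction of the next card from the previous ones. Participants can tell water from a flavoured drink, they stay in the endoscopy room, and a nurse then takes their visual analogue scores, so past assignments could reach study staff. There is one site, and the stratum of each patient is visible.

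What is at stake is concealment at enrolment. Patients are approached again and consented on the day, so someone who knew the next assignment could let it influence who is entered.

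**Working it through.** **Inputs.** Block size 6, ratio 1:1 and two gender strata (Sampling method and subject recruitment); 39 per group, 78 in total (Sample size estimation). The Protocol gives no predictability figure to reproduce. The gender split is not stated, so 39/39 and 36/42 are used as assumptions.

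**Forced allocations in a full block of 6.** There are C(6,3) = 20 equally likely sequences of three A and three B. A place is forced once one arm has used its three slots.
- Sixth place: always forced, probability 1.
- Fifth place: forced if the last two places are the same arm, 8/20 = 0.4.
- Fourth place: forced if the first three are the same arm, 2/20 = 0.1.
- First to third places: never forced.

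The sum is 1 + 0.4 + 0.1 = 1.5 of 6, or 25%. The closed form for a block of 2m agrees: 2m/(m + 1) = 6/4 = 1.5.

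**Across the trial.**
- 39/39 split: each stratum has 6 full blocks and 3 patients in an incomplete block. Forced: 6 × 1.5 + 0 = 9 of 39, or 23.1%. Both strata: 18 of 78.
- 36/42 split: 6 + 7 = 13 full blocks. Forced: 13 × 1.5 = 19.5 of 78, or 25.0%.
- Over all splits with at least 10 patients per stratum, the range is 23.1% to 25.0%.

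**With sizes that vary.** The size sets are assumptions. The simulated observer has the full history of a stratum of 39, knows which sizes are in use, and does not know the size of any given block.

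| Block sizes | Allocations known with certainty |
|---|---|
| 6 only | 23.1% |
| 4 and 6 | about 5.6% |
| 4, 6 and 8 | about 2.3% |

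**Best guess.** Guessing the arm that is behind (a coin toss when level) needs no knowledge of block size. Over a full block of 6 it is right 4.1 times in 6, or 68.3%. Over 39 patients the expected count is 6 × 4.1 + 1.7 = 26.3, or 67.4%. With sizes 4, 6 and 8 mixed, simulation of 39 patients also gives 67.4%. Varying the sizes removes certainty and leaves this guess as accurate as before.

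**The case against.** The 23–25% applies only to someone who knows every earlier allocation in the stratum and where the blocks start. The Protocol gives no member of the enrolling or assessing team such a record. The list-maker and the person preparing the drink stand outside the trial's clinical work, the envelopes are sealed and numbered, and the containers are identical. Eligibility is simple, and the text shows no motive for steering patients. A fixed permuted block with third-party preparation is a legitimate design, and the word random may be a slip of language. All of this stands, and it keeps the point minor.

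Two stronger readings are tempting. A reader might infer that concealment has failed. The documents do not support that: they show a route by which past assignments could become known, but nothing says that anyone is told them or tallies them. A reader might also infer that the block size undermines the blind of the endoscopist or the nurse. If a participant reveals the drink by its taste, staff are unblinded for that patient whatever the block length, and varying the sizes would not repair it. What the block size adds lies mainly at enrolment.

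The objection does not remove the core. The Protocol names a property that its own figure excludes, and the safeguards protect the next card but not inference from past ones.

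**Conclusion.** The point holds as a minor one. The block size is fixed at 6 and disclosed, despite the word random. For an observer who knows the earlier allocations in a stratum and where its blocks start, 25% of allocations per full block are certain, and 23% with 39 patients per stratum: about 18 to 19.5 of the 78 for the two gender splits shown. How far any observer would in fact come to know those allocations cannot be judged from the Protocol. No effect on the gastric-volume comparison, its type I error or its power has been shown, and the sample size is unaffected.

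**What to change.** Generate the list with at least two block sizes in random order within each gender stratum, for example 4, 6 and 8. In the Protocol, say only that block sizes vary and are withheld from site staff, and keep the sizes in the list-holder's file. Sizes 4 and 6 alone would leave about 6% certain, against about 2% with 4, 6 and 8, if the set became known.

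The cost is one setting when the list is made, and a possible final imbalance of a few patients per stratum. An incomplete block can leave a difference of at most half its length: 4 patients for a block of 8, against 3 for a block of 6.

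The Protocol speaks of the sequence in the past tense, so the list may already exist. In that case, apply the change to the unused part of the list. Otherwise delete the word random, state the fixed size of 6, and report it as a limitation.

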### **Research tools**

1. Data collection pro forma
2. Resource beverage (53.6g carbohydrate and 9g whey protein), plain water
3. Visual analogue scale for assessment of patient well being
  - Each scale consisted of ungraded, horizontal lines anchored at two ends.
  - The left end of the scale represented “not at all” which score: 0 and the right end represented and “the most imaginable” which score: 100
  - patients mark an X somewhere along the horizontal line to complete the scale
4. OGDS
5. 2 Suction systems (include suction reservoir, yankauer sucker)

### **Data collection method**

All subjected planned for OGDS with the complain of one or more of the following symptoms: Bothersome postprandial fullness, early satiation, Epigastric pain or Epigastric burning and fullfill inclusion criteria are selected. Patients will be approached and be explained regarding the study in

surgical outpatient clinic prior to OGDS. Patient will be approached again on the day of OGDS, if agree to participate, an informed consent will be obtained. Informed consent will be obtained after explanation regarding the study and procedure again by researcher nurse

Allocation sequence is according computer generated random number list, it was prepared by an investigator with no clinical involvement in the trial. Allocation sequence was concealed from researcher enrolling and assessing participants. Allocation sequence will be sealed in sequentially numbered and opaque envelopes. A manila card will be placed inside envelop to render it impermeable to intense light. To prevent subversion of the allocation sequence, the name and I/C of the participant will be written on a book together with the series number on envelopes. The details in the book will be kept confidentially. After enrolled subject complete all baseline assessment, corresponding envelope will be enclosed by staff (who not involve in study) who prepare the drink. The staff need to ensure that the envelop still sealed when receive it. The staff will prepare the drink into identical container according to the assignment.

Subjects are randomised into 2 group: 1 group with 250cc plain water and another group give 1 packet resource(237ml). Subjects need to finish the drink over 10minutes. After that, subjects are not allow to leave endoscope room before OGDS done to prevent consumption of other drink or food.

2 hours after that, subject undergo OGDS. OGDS is done follow standard protocol.

1. Patient lies in left lateral position
2. Medication to numb the back of throats (spray) will be given to prevent gagging during the passage of the instrument
3. A plastic mouth guard is placed between the teeth to prevent damage to the teeth and endoscope.
4. The endoscope (also called a gastroscope) will be inserted through the mouthpiece

[figure not shown]
5. A small container or yankauer suction is placed close to the mouth of a patient to collect saliva during and after the esophagogastroduodenoscopy
6. Endoscope will be inserted along the middle line of the soft palate.
7. Once endoscope advanced, patient may be asked to swallow to facilitate advancement of scope.
8. Throughout the procedure, no water flushing is allowed, only air inflation is allowed
9. visualised pooling of fluid in the stomach is aspirated until dry via direct visualization with endoscope. Aspirated fluid will be collected in suction reservoir and the fluid will be measured.

Subject's wellbeing is assessed via visual analogue scale (VAS) which consist of 5 parameters: hunger, thirst, anxiety, tiredness and weakness. This scale will be used repeatedly during this study to assess patient's wellbeing. Trained staff nurse will ask patient regarding level of 5 parameters and subject need to mark X somewhere along the horizontal line given before drink and before OGDS procedure.

All subjects are advised to inform assessor if there is adverse reaction. Medical personnel are available to manage any adverse events that might occur throughout the procedure.

The possible risk that may arise in the study include injury to the gastrointestinal's wall, aspiration and bleeding which is the similar risk for all patient going through OGDS procedure. Small volume of the drink will not cause psychological distress to subject, but its taste may not be palatable.

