# The effect of carbohydrate loading on gastric residual volume and hunger score

## Introduction

ERAS (enhanced recovery after surgery) protocol is a standardised perioperative care procedure which aim to improve patient outcome(Carmichael *et al.*, 2017). It can be divided into preoperative, intraoperative and postoperative components. One of the measures in preoperative care component is carbohydrate loading. Carbohydrate loading is usage of carbohydrate rich beverage prior to operation to improve insulin resistance post operation(Faria *et al.*, 2009). Body response to surgery and prolong fasting by releasing of stress hormone and inflammatory marker(Kratzing, 2011). This led to insulin resistance and catabolic state(Kratzing, 2011). Production of glucose via gluconeogenesis and inability of usage of glucose by peripheral tissues due to insulin resistance cause hyperglycaemia post operation(Kratzing, 2011). This catabolic state and insulin resistance are associated with increased morbidity and mortality postoperatively(Gustafsson *et al.*, 202308; Tran *et al.*, 2013). By giving carbohydrate loading prior operation shift body metabolic from fasted state into fed state(Tran *et al.*, 2013).

Recent guideline had recommended to allow solid food until 6 hours prior to and clear fluid 2 hours prior to operation in replace to fasting of minimum of 6 hours(Kratzing, 2011). However, most of the centres still practice nil by mouth for minimum of 6 hours due to worried of pulmonary aspiration. According to previous study, patient are at risk of develop pulmonary aspiration if the gastric content >25ml (>0.4ml/kg) and the pH<2.5(Dalal *et al.*, 2010). Pulmonary aspiration is a fatal complication for patient undergoes general anaesthesia. It is due to aspiration of acidic gastric content during intubation and subsequently leads to pneumonitis(Nason, 2015). There are several normal physiological reflex mechanism to prevent aspiration of gastric content but they were abolished by

the drugs used during general anaesthesia(Robinson and Davidson, 2014). Apart from residual gastric volume and pH, delay gastric emptying in patient who has diabetic mellitus, dyspepsia, history upper gastrointestinal surgery or intestinal obstruction can predispose to pulmonary aspiration also(Asai, 2004).

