According to study, amount of carbohydrate that can stimulate insulin release is 50g(Kratzing, 2011). Carbohydrate rich beverage contained polymer (maltodextrin) is used as carbohydrate loading currently because its low osmolality compared with other monomer beverage(Nygren *et al.*, 1995). Low osmolality leads to increase gastric emptying rate(Nygren *et al.*, 1995). However, absorption of small bowel for glucose from digested maltodextrin is rapid, which affect blood sugar level especially in diabetic patient(Hofman *et al.*, 2016).

There is still no proper guideline regarding usage of carbohydrate loading in diabetic mellitus patient prior to operation in view of possibility of delay gastric emptying and poor glycaemic control after loading(Gustafsson *et al.*, 2008).

Other than metabolic effect, carbohydrate loading also improve patient's wellbeing in the aspect of thirst, hunger and anxiety in most of the study(Gustafsson *et al.*, 2008; Hausel *et al.*, 2001).

Most studies conducted showed carbohydrate loading prior to operation is safe and benefit. However, most of studies conducted to measure gastric volume is through aspiration via nasogastric tube. This study conducted is to assess effect of carbohydrate loading (maltodextrin with whey protein) to gastric volume 2 hours after ingestion via aspiration while doing OGDS (direct visualisation) and patient's wellbeing (hunger, thirst, weakness, tiredness, anxiety) for all patient planned for OGDS.

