Glucose from maltodextrin is rapidly reabsorbed by intestine and causes elevation of blood glucose rapidly (Hofman *et al.*, 2016). It may impair blood glucose level in diabetic mellitus patient. There is a study about use of carbohydrate loading in diabetic mellitus patient, which showed higher peak glucose level which occurs later and takes longer time for blood glucose to return to baseline if compared to healthy subject (Gustafsson *et al.*, 2008). Because of the possibility of impaired blood sugar and delayed gastric emptying in diabetic mellitus patient, use of carbohydrate loading in diabetic mellitus patient is still debated.

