**Community sensitivities and benefits**

This study finding may benefit the community by knowing the effect of carbohydrate drink before procedure on patient's well being and its safety to be used in future.

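### The risk statement names taste as the drink's only possible drawback although the background describes glycaemic effects in eligible patients, and the pro forma has no field for adverse events

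*Protocol*

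**What the plan says.** **Risk statement (Protocol, Data collection method).** The risks that may arise are said to include "injury to the gastrointestinal's wall, aspiration and bleeding which is the similar risk for all patient going through OGDS procedure". On the drink, the next sentence reads "Small volume of the drink will not cause psychological distress to subject, but its taste may not be palatable". The same section asks all subjects to tell the assessor of any adverse reaction and says that medical personnel are available.

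**Background on the drink.** The Introduction says that glucose from digested maltodextrin is absorbed rapidly, "which affect blood sugar level especially in diabetic patient". It says that there is no proper guideline for loading in diabetic patients "in view of possibility of delay gastric emptying and poor glycaemic control after loading". The Literature review repeats the point on glucose ("It may impair blood glucose level in diabetic mellitus patient"), describes a study with a higher and later glucose peak and a slower return to baseline in diabetes, and concludes that "use of carbohydrate loading in diabetic mellitus patient is still debated".

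**Who takes part and what they take.** Subject criteria lists four exclusions: previous upper gastrointestinal surgery, intestinal obstruction, vomiting, and inability to consent. Diabetes is not among them. Under Sampling method and subject recruitment, group B drinks one 237 ml pack with 53.6 g of carbohydrate and 9 g of whey protein.

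**What is recorded.** Research tools names the pro forma as the collection form, and it is reproduced at the end of the Protocol. It holds demographics, the times of drink and scope, the residual volume, and the visual analogue scales at two time points.

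**What is hoped for.** Community sensitivities and benefits says that the community may benefit from knowing "the effect of carbohydrate drink before procedure on patient's well being and its safety to be used in future".

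**The concern.** There are two linked problems.

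First, the risk statement is not in step with the rest of the Protocol. The background attributes a specific effect to this type of drink in a specific group of patients. That group can be enrolled, and half of those enrolled receive the drink. Yet the passage that tells the site what might go wrong does not mention glucose.

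Second, subjects are asked to report reactions, but the trial's form gives nowhere to write them down. Events that are not collected in a standard way cannot be tabulated by arm later, whatever an analysis plan says. A trial that hopes to inform on the drink's safety would then have only the residual volume to show for it.

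**Working it through.** **1. Risk statement against background**

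| Topic | Background sections | Risk statement |
|---|---|---|
| Blood glucose after the drink | Rapid rise; possible poor control in diabetes | Not mentioned |
| Gastric emptying after the drink in diabetes | Possible delay | Not mentioned |
| Use in diabetic patients | Still under debate | Not mentioned |
| Taste | – | May be unpalatable |

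Subject criteria does not remove the patients in the first three rows, so the gap concerns people who can be randomised.

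**2. Reporting against recording.** Going through the pro forma field by field (ID, randomization, age, gender, weight, height, BMI, time of drink, time of scope, residual volume, five scales before the drink, five before the scope):
- adverse-event fields: 0
- glucose fields: 0
- diabetes-status fields: 0

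**3. The Protocol's sample size.** Inputs from Sample size estimation: difference 12.5 ml, SD 18.46, two-sided 5%, power 80%, ratio 1:1.
- n per group = 2 × (1.960 + 0.842)² × 18.46² / 12.5² = 2 × 7.849 × 340.77 / 156.25 = 34.2, rounded up to 35.
- With 10% dropout: 35 / 0.90 = 38.9, rounded up to 39.

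Both match the stated figures. Nothing in this point changes them.

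**4. What recorded events could show at this size.** If no event of a given kind is seen among n subjects in an arm, the one-sided 95% upper bound on its rate is 1 − 0.05^(1/n).
- n = 39: 1 − 0.05^(1/39) = 0.074
- n = 35 (if the full 10% drop out): 1 − 0.05^(1/35) = 0.082

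The chance of seeing at least one event among 39 is 1 − (1 − p)^39. The Protocol gives no event rate, so p is an assumption:

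| Assumed rate p | Chance of at least one event in 39 |
|---|---|
| 1% | 32% |
| 2% | 55% |
| 5% | 86% |

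Only fairly common events could be excluded, so any safety statement should be modest even with full recording.

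**The case against.** **The aspiration statement.** A reader might infer that describing the aspiration risk as similar is also contradicted, because the Introduction says that "patient are at risk of develop pulmonary aspiration if the gastric content >25ml (>0.4ml/kg) and the pH<2.5" and residual volume is the primary end point. The documents do not support this.
- The comparison is with patients having OGDS in general, not with the water arm.
- The criterion needs low pH as well as volume, and it is set out in the context of general anaesthesia. The procedure described here uses throat spray.
- The Introduction says that most studies found loading safe, and the Literature review calls clear fluid up to 2 hours before operation safe.

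Nor can the gap be sized from the Protocol's figures. Under a normal model with SD 18.46, the share above 25 ml is about 15% at the 5.5 ml mean cited for water and 35% at 5.5 + 12.5 = 18.0 ml. But the 5.5 ml mean comes from a study with its own SD of 3.70, while 18.46 comes from an article that is not named. Together they would make about 38% of water volumes negative. With SD 3.70 the shares are about 0% and 3%. At the 17.1 ml mean that the same study gives for fasted patients, SD 18.46 gives (25 − 17.1) / 18.46 = 0.43, or about 33%, close to the 35%. The 12.5 ml is also a difference chosen for a two-sided test, not a predicted increase.

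**Other points for the plan.**
- The risks are said to include the listed items, so the list is not offered as complete.
- Events may be written in clinical notes, so it would go too far to say that they will be lost.
- Safety is neither an objective nor an end point, and the benefit sentence says only that findings may help. Safety there could mean residual volume.
- Tables of events are commonly left to an analysis plan.
- The consent pages are not available, so nothing can be said about what subjects are told.

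These points limit the finding but do not remove it. A non-exhaustive list that mentions taste and omits glucose is still out of step with the background. Clinical notes are not trial data collected in the same way in both arms. The missing field is on the Protocol's own form, not in an analysis plan.

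**Conclusion.** The point holds in two parts. The risk statement omits the glycaemic and gastric-emptying effects that the Protocol itself attributes to carbohydrate loading in diabetic patients, who are eligible. The pro forma has no place for the adverse reactions that subjects are asked to report, so a comparison by arm is not possible from the form as it stands.

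Its size is modest. The primary comparison and the 39 per group are untouched. What is lost is any direct evidence on safety, and that evidence would be limited in any case: an upper bound of about 7.4% after zero events in 39, or 8.2% in 35. The conclusion assumes that the pro forma shown is the complete form and that no separate event log exists; the Protocol mentions none.

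A reader might also infer that diabetic patients should not be enrolled. The documents do not settle that. It is a clinical decision, and the point here is only that the passages must agree.

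**What to change.** 1. Reconcile the risk statement in Data collection method with the Introduction, the Literature review and Subject criteria. The investigators decide how; no clinical rule is proposed here.
2. Add one line to the pro forma: adverse event none/yes, what it was, and time since the drink. The blinded assessor, to whom subjects already report, completes it. The form has a field headed Randomization; if that field is to hold the arm, the line should be completed before it is filled in.
3. Tabulate events by arm beside the residual volume.
4. Limit the safety statement in Community sensitivities and benefits to what was recorded, and note that about 39 subjects per arm can exclude only common events.

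The cost is a wording change, one form line and one table, with no added staff, procedure or subjects. The line has to be in place before data collection, because events not recorded at the time cannot be reliably recovered afterwards.
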